#### **Specific Aim 2:**

To evaluate the impact of TCS to support chronic disease self-management in patients with Long COVID living in low-income Hispanic communities in Puerto Rico on self-efficacy, disease monitoring, use of health care services, medication use and risk behaviors. To do this we will evaluate the implementation of **“Tomando control de su salud”** (TCS) among patients with Long COVID and chronic diseases participating in the PR-COAS cohort study, and the changes (if any) in data related to measures of chronic diseases management, included data from the baseline interview and follow up interviews before and after this implementation. We will use Kirkpatrick's evaluation model as a framework and guide in analyzing the impact of the TCS program on the participants' self-management of chronic diseases. This model has been widely used for evaluating participants' outcomes in training programs, including research studies aimed to evaluate training programs regarding self-management of chronic health conditions. Like

other chronic diseases self-management related studies that have applied this evaluation model,

, we will use in our study the first three levels of this model as follows:

1. Reaction - At this level, we will evaluate the degree of satisfaction and perception of the participants regarding the TCS program; we will seek to know their opinion and experience about TCS. To do this, we will use data from the TCS program's final survey, titled Formulario Final (Post-Prueba & Evaluación). It includes close-ended questions regarding the TCS sessions' attendance, general satisfaction with the discussed topics and leaders' evaluation, and an open-ended question about the experience participating in the TCS program (the study participants can express their feelings, ideas, opinions, comments or reactions after having participated in the program).

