The last interview of the cohort study (PR-COAS) in which the participants will be identified, which collect information on general aspects of self-care of chronic diseases, healthcare utilization, vaccination status, lifestyles modifications, and health-related quality of life among others, will be used as baseline for the purposes of this study. In addition, a follow up interview will be coordinated one month after completing TCS for the intervention group and approximately 3 months after the last interview of the cohort study for the control group. The following indicators will be collected: Health care services utilization (primary care, emergency room and hospitalizations), compliance with prescribed medications, risk behaviors (such as smoking, physical activity, alcohol use), nutritional awareness, self-efficacy for disease management based on the level of confidence) and quality of life. The standard data collected by the PRDOH for this intervention (*Formulario 1: Formulario Inicial, Preprueba, and Formulario 2: Formulario Final, Post-Prueba & Evaluación, Rev. Enero 2022*) will also be used for analysis. The Form 1 is a self-administered questionnaire of 28 closed-ended questions that collects TCS participants' sociodemographic and contact information (name, municipality of residence, marital status, education, age, sex, medical plan, email), general information on diagnosed health chronic conditions, COVID-19 vaccination, level of confidence in managing chronic conditions, general health, use of health services, and lifestyles (e.g. consumption of vegetables, fruits and alcoholic beverages, physical activity and whether or not you smoke). The Form 2 is a 40-question self-administered questionnaire that mainly collects general information about the lifestyles of TCS workshop participants (consumption of vegetables, fruits and alcoholic beverages, physical activity and whether or not they smoke), general health status, level of confidence in managing health chronic conditions, utilization of health services, attendance, evaluation and experience in TCS workshop.

The impact of health-related quality of life will be assessed using the following scales:

- EQ-5D-5L (Spanish version), which includes five dimensions: mobility, self-care, daily activities, pain or discomfort, and anxiety or depression.
- Fatigue (NIH PROMIS® Neuro-QoL Item Bank v1.0, Short Form, Spanish version)

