**Data analysis:** Since this is a pilot study the primary focus of the statistical analysis of this study is estimation (effect sizes and associated uncertainty). We will conduct pre- and post-intervention analysis among participants of the intervention group and between group comparisons with intervention and non- intervention groups. Descriptive analyses will be done using frequency distribution and contingency tables for categorical data. Continuous variables will be reported using mean, median, standard deviation, inter-quartile range and range. Chi-square or Fisher's exact test will be done to assess differences in sociodemographic or health indicators between the groups and to compare the independent domains of the quality-of-life scale among patients in the intervention or non-intervention group. To evaluate changes in quality of life before and after the intervention, estimates and 95% confidence intervals will be generated based on the change scores, i.e., using paired data with each subject acting as their own control. Estimates and confidence intervals will be provided for both the individual group changes as well as the difference in change between each pair of groups. We will perform Wilcoxon/Mann-Whitney U-tests (non-parametric) comparing the change scores in each group with each other. These Wilcoxon tests will be performed in addition to a Kruskal-Wallis test (non-parametric ANOVA) in order to test for an overall group effect. The Wilcoxon paired sample test will be used for ordinal data and the Mc Nemar test for significant changes will be used to evaluate dichotomous data. All analyses will be conducted using Stata version 11(Stata Corporation, College Station, Texas, USA).

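### No between-arm comparison of change is specified for yes/no Aim 2 outcomes, so a change shared by both arms could be read as an effect of the workshops

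*Combined protocol and SAP*

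**What the plan says.** Specific Aim 2 is to evaluate the impact of TCS "on self-efficacy, disease monitoring, use of health care services, medication use and risk behaviors". In METHODS, the paragraphs on outcome measures list the variables: "The following indicators will be collected: Health care services utilization (primary care, emergency room and hospitalizations), compliance with prescribed medications, risk behaviors", followed by others such as nutritional awareness and self-efficacy.

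The Data analysis paragraph of METHODS contains five relevant statements:

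- A general one: "We will conduct pre- and post-intervention analysis among participants of the intervention group". The same sentence goes on to promise "between group comparisons with intervention and non- intervention groups", without naming an outcome or a method.
- For categorical data between groups: "Chi-square or Fisher's exact test will be done to assess differences in sociodemographic or health indicators between the groups". The same sentence adds the separate domains of the quality-of-life scale. It gives no time point.
- For change: "To evaluate changes in quality of life before and after the intervention, estimates and 95% confidence intervals will be generated based on the change scores".
- Directly after that, estimates and intervals are promised for each group's change and for "the difference in change between each pair of groups". Mann-Whitney and Kruskal-Wallis tests on the change scores follow.
- For yes/no data: "Mc Nemar test for significant changes will be used to evaluate dichotomous data".

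The paragraph opens by saying that, in a pilot, the main purpose of the analysis is to estimate effects and their uncertainty.

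**The concern.** Aim 2 is about impact, and the protocol recruits a control group to assess it. For a yes/no outcome, such as any emergency room visit or current smoking, the quantity that uses that group is the change in proportion under TCS minus the change in proportion under control. The plan names no method that clearly gives this. McNemar does not use the control arm. A chi-square or Fisher test compares levels at one time point. At baseline it says nothing about change, and at follow-up it carries forward any difference the arms started with.

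That matters here because the controls are the people who declined the workshops. Change within the TCS arm can include regression to the mean, recovery from Long COVID and calendar effects, some or all of which the control arm may share. A significant McNemar result in one arm beside a non-significant one in the other does not show that the arms differ.

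**Working it through.** The documents give no power, test level, effect size or calculated sample size, so there is no figure of the plan's own to reproduce. What follows is illustrative.

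**Inputs from the documents.** The sampling strategy in METHODS expects 20-25 participants in the intervention arm and 30-40 in general care. Allocation is not randomized.

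**Assumptions (not in the documents).** Tests are two-sided at 0.05. The workshops are pooled as one TCS arm. The probabilities of improving and of worsening are the same in both arms, so TCS has no effect. Improvement ranges from 20% to 40% and worsening from 5% to 10%.

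**Within-arm test.** With b improving and c worsening, the exact McNemar p-value is min(1, 2·P(X ≤ min(b,c))), where X is binomial(b+c, ½). The chance of significant improvement is the multinomial probability summed over all (b,c) with b > c and p < 0.05.

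**Between-arm test.** The difference is D = (b₁−c₁)/n₁ − (b₀−c₀)/n₀. Its variance is the sum over arms of [(b+c)/n − d²]/n, where d = (b−c)/n. The simulation (20,000 trials per row) used n−1 as the outer divisor and a Wald test.

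| Improve / worsen, both arms | TCS / control n | McNemar: significant improvement in TCS arm | Difference in change: significant for TCS | Difference in change: two-sided |
|---|---|---|---|---|
| 20% / 5% | 20 / 30 | 9.5% | 2.5% | 5.7% |
| 20% / 5% | 25 / 40 | 16.5% | 2.3% | 5.4% |
| 30% / 5% | 20 / 30 | 32.1% | 2.9% | 5.9% |
| 30% / 5% | 25 / 40 | 45.7% | 2.6% | 5.4% |
| 35% / 5% | 20 / 30 | 45.5% | 2.9% | 5.7% |
| 35% / 5% | 25 / 40 | 60.2% | 2.9% | 5.9% |
| 40% / 5% | 20 / 30 | 58.2% | 3.1% | 5.9% |
| 40% / 5% | 25 / 40 | 72.5% | 3.0% | 5.7% |
| 30% / 10% | 20 / 30 | 17.4% | 2.9% | 5.7% |
| 30% / 10% | 25 / 40 | 24.2% | 3.0% | 5.8% |

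The McNemar column is not a false-positive rate for McNemar itself, because the arm really does change. It is the chance that a shared change looks significant when the TCS arm is viewed alone. The plan does not say whether the exact or the large-sample form is meant. With the large-sample form the same column runs from 26.0% to 80.7%.

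**Two constructed examples.** The counts are not from the documents.

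1. *Both arms change alike.* TCS: 8 improve, 1 worsens, of 24; p = 2(1+9)/2⁹ = 0.039. Control: 12 improve, 2 worsen, of 36; p = 2(1+14+91)/2¹⁴ = 0.013. D = 7/24 − 10/36 = 0.292 − 0.278 = 0.014. Variance = (9/24 − 0.292²)/24 + (14/36 − 0.278²)/36 = 0.0121 + 0.0087 = 0.0207. The 95% CI is −26.8 to +29.6 points.
2. *One arm significant, the other not.* TCS: 6 improve, 0 worsen, of 22; p = 2/2⁶ = 0.031. Control: 8 improve, 2 worsen, of 35; p = 2(1+10+45)/2¹⁰ = 0.109. D = 6/22 − 6/35 = 0.273 − 0.171 = 0.101. Variance = (6/22 − 0.273²)/22 + (10/35 − 0.171²)/35 = 0.0090 + 0.0073 = 0.0163. The 95% CI is −14.9 to +35.2 points, p = 0.43.

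**Fisher test at follow-up only.** If both arms stand at 65%, it is significant in 3.5-3.7% of trials. If a 20-point baseline gap merely persists (65% against 45% at follow-up), it is significant in 26% of trials at 20/30 and 32% at 25/40, although neither arm changed more than the other.

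**The case against.** The strongest reply is that the plan does have controlled comparisons. It promises comparisons between intervention and non-intervention groups and names chi-square or Fisher tests for health indicators. METHODS uses the word indicators for the Aim 2 variables, and Aim 2 says the before-and-after data will be compared with a control group present. This stands as far as it goes: a reader who infers that yes/no outcomes are tested only within the TCS arm goes beyond the text. But the general promise names no method, and the chi-square or Fisher test is not a test of change at any time point.

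Second, the sentence on the difference in change between pairs of groups carries no restriction of its own, so it might be meant for every outcome. That reading is possible. The sentence follows one limited to quality of life, however, and yes/no data are then given McNemar with no between-arm counterpart. The scope is at best unclear.

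Third, nothing says that a McNemar result alone would be reported as impact. A reader might infer that the plan will declare a TCS effect on that basis. The documents do not support this: the study is described as unpowered and focused on estimation. The risk is that the result could be read that way. Pilot status does not remove the gap, because the missing item is an estimate with an interval, which is what the pilot says it is for.

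Fourth, response formats are not given, and self-efficacy and disease monitoring have multi-item instruments. How many Aim 2 outcomes are yes/no is unknown.

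**Conclusion.** The point holds in a limited form. The Data analysis paragraph specifies no between-arm comparison of change for yes/no Aim 2 outcomes. What it offers is a within-arm McNemar test, or a comparison of levels at an unstated time that does not account for baseline differences between self-selected arms.

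At the planned sizes the consequence can be large. Where both arms change equally, the TCS arm alone would show significant improvement in about 10-73% of trials per outcome, against 2.3-3.1% in favour of TCS for the difference in change. These figures rest on assumed rates, a two-sided 0.05 level and the exact McNemar test. They show how far a shared change could mislead and do not predict this trial's results. They apply only to outcomes recorded as yes/no.

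A between-arm estimate would not settle causation either. The arms are self-selected, and follow-up is one month after the workshops for TCS but about three months after the last cohort interview for controls.

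**What to change.** Add to the Data analysis paragraph that, for each yes/no Aim 2 outcome, the TCS-minus-control difference in the paired change in proportion will be reported with its 95% confidence interval, computed directly as the difference of the two paired differences. If GEE is preferred, specify an identity link, so that the arm-by-time term is a difference in proportions, and small-sample standard errors. Base the between-arm Aim 2 statement on this estimate and label McNemar as within-arm description. State the time point and purpose of the chi-square and Fisher tests. Add that self-selection and the different follow-up timing prevent attributing the difference to TCS alone.

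The cost is a short addition to the text and one extra estimate per outcome, from data already to be collected. Intervals will be wide at these sizes, and some apparent effects may no longer look significant.

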## HUMAN SUBJECT PROTECTION

**Consent process:** After the patient expresses interest in participating in the study, study staff will contact the potential participant via phone or face to face to discuss the study informative sheet following the appropriate consent process as described in the method section. The consent process will be done only by the investigators, study staff, or trained interviewers. The study coordinator will oversee the training of the interviewers about the process of consent by the discussion of the informative sheet and the study procedures prior to any contact with potential participants. A script will be developed to explain the process of consent over the phone. The information in the script will include the purpose of the study, duration of subject participation, description of the procedures, risks, benefits, and confidentiality. In addition, it will include information about the voluntary nature of participation and whom to contact for questions. During the process, the subjects will have the opportunity to ask questions, and if the potential participant requests any other information about the study, it will be provided. Although a written consent form will not be collected, the person who will conduct the discussion of the informative sheet should document all the activities, including the date and time of the call, duration, and if there were questions regarding the process. The person in charge of the consent process should also document and certify in a form that the information provided by them is correct and that the subject consented.

Participants will receive an incentive for transportation and/or parking expenses and for the time dedicated for their participation. The intervention group will receive \$25 for each session of the TCS workshop. This incentive will be given to them at the end of each session at the Endowed Health Services Research Center (EHSRC). Upon completion of the final interview, one month after the end of the workshop, the participant will receive a \$25 incentive that can be sent to them by certified mail or can be hand-delivered at the EHSRC office in a specific time scheduled. In the

case of the non-intervention group, participants will receive a \$25 incentive upon completion of the final interview, approximately 3 months after completing the baseline interview, that is, the final PR-COAS interview.

**Benefits:** This study does not directly benefit the person for their participation. Participating in this study has not cost. Although participants would not derive any direct benefit, the potential benefit to society is an increased understanding of the factors associated with post-COVID19 sequelae in our population, critical information for making patients guidelines, and public health recommendations and decisions. In addition, the participants will receive information about the general management of management of chronic disease that could be of benefit for them.

**Risks:** This study poses minimal risk to the study participants. There could be some risk to the privacy and confidentiality of the participants as part of their participation in group discussions. Also, there could be some discomfort on answering some of the questions in the interview. We do not expect the participant to be harmed or have any additional risk as a result of their participation in the study. The intervention and the interviews will be done by trained personnel that will let the participant know they can stop their participation at any moment or refuse to answer a question. This will not affect the participants' rights, or the clinical services received at the healthcare center.

**Privacy and confidentiality:** All study-related data will be maintained confidential with restricted access only available to the PI, project coordinator, and designated study staff. All study procedures, including the phone interviews, will be done in a private location at the Office of Clinical and Community Health Research. Confidentiality of participant's information will be assured. Participants' contact information will be collected and is needed to coordinate the follow-up interviews. This information will be collected in the screening registry and will include the name,

telephone numbers, residential and postal address, email, Facebook account, and preferred contact method. This form will be collected in an electronic database and kept separated from the study questionnaire. The contact information collected from interested participants will not be shared or disclosed with other people or organizations.

This protocol will be modeled after our previous studies, which used a REDCap tracking database to minimize any breach in subject's confidentiality. We will keep a separate file that includes only the patient's study identification number. All documents in the form of hard copies will be kept in safely locked cabinets located in the PI's office at the Office of Clinical and Community Health Research located at the Hospital UPR in Carolina, whereas all electronic data will be kept on a secured server at UPR School of Medicine with multiple levels of password protection (encrypted files in password-protected computers) to which only the investigators will have access. The entire research staff has completed the human subjects' protection and the management and security of health information certification process as required by the IRB of the UPR. It will receive extensive study-specific training in data collection and transfer. A request for a waiver of authorization for the release of health information will be completed. At the end of the data collection process and following up of the patients and database cleaning, all personal identifiers will be removed, and the final database for analysis will be anonymized. After five years, all data in the form of hard copies will be shredded.

**TABLE 2: PROPOSED TIMELINE**

		9 - Months								
Proposed Activities		1	2	3	4	5	6	7	8	9
Intervention for Long-COVID – chronic disease self-management	Training or recruitment of trainers for “Tomando Control de su Salud” intervention	X	X							
	Submission and approval of IRB		X	X						
	Participant selection and group allocation				X	X	X			
	Intervention workshops (8 – 12 participants)							X	X	
	3-month follow-up interview								X	X
	Data analysis and dissemination							X	X	X

